6.1.8. Clinical Laboratory Tests

The following laboratory parameters will be measured at screening and at the time points specified in the Schedule of Assessments ([Table 1](#) and [Table 2](#)) and will be analyzed locally or centrally by a certified laboratory:

- A serum pregnancy test during screening for all women of child-bearing potential (WCBP)
- Serum or urine pregnancy testing for all WCBP prior to each dose
- Hematology laboratory parameters include WBC count, hemoglobin, hematocrit, PLT count, and WBC differential
- Blood chemistry laboratory parameters, including blood urea nitrogen, creatinine, glucose, AST, ALT, ALP, bilirubin (total and direct), electrolytes (sodium, chloride, bicarbonate, potassium), amylase, lipase, albumin, magnesium, calcium, and phosphorus
- Coagulation laboratory parameters, including prothrombin time, partial thromboplastin time or activated partial thromboplastin time, and international normalized ratio
- Complete urinalysis with qualitative analysis for protein (dipstick)
- Human immunodeficiency virus (HIV), hepatitis B (HBV) (HBsAg, anti-HBc and anti-HBs), and hepatitis C (HCV) testing (screening only)

The following laboratory tests will be performed centrally at screening as specified in the Schedule of Assessments ([Table 1](#) and [Table 2](#)):

- HLA DQ2.5 and HLA DQ8 testing
- Transglutaminase (tTG) and deaminated gluten peptides (DGP) IgA/IgG

For tTG, a result of <2x ULN will be considered negative or weak positive. For DGP, a result of <30 U/mL will be considered negative or weak positive.

For re-screening, the HLA does not need to be repeated and the tTG and DGP antibody tests should only be repeated if >3months have elapsed from end assessment.

Unscheduled assessments should be performed as clinically indicated.

For any out-of-range laboratory findings during screening, repeat laboratory testing may be performed at the discretion of the Investigator. Abnormal laboratory findings at screening should be recorded as medical history only if considered CS.

Clinical laboratory assessments should be performed prior to KAN-101/PBO infusion when applicable.

Laboratory findings assessed by the Investigator as CS, including but not limited to, those findings resulting in a drug interruption/hold/reduction/discontinuation or medical intervention, should be repeated to verify the out-of-range findings, followed to a satisfactory clinical resolution, and reported as an AE(s) (see [Section 11.1.1](#) for definition of an AE).

6.1.9. KAN-101 Administration

Detailed instructions on the administration of KAN-101 can be found in [Section 10](#).

CCI

6.1.11. Gluten Challenge

All patients enrolled in Part B of the study will undergo a GC for 3 days, from D15 to D17. During these 3 days, patients will self-administer 9 g of gluten protein orally (PO) once each day at approximately the same time every morning. The first dose of gluten will be administered in the clinic, and the patient will be observed for at least 6 hours to monitor for hyperacute reactions requiring medical treatment and collection of biomarker samples. Patient compliance will be recorded by the study Investigator.

6.1.12. Pharmacokinetic Sampling

PK sample collection time points are shown in [Table 1](#) and [Table 2](#).

The exact date and time of each sample collection must be recorded for all collected samples.

Refer to the KAN-101-01 Laboratory Manual for details on processing, storage, and shipment of PK samples.

CCI

6.1.14. Adverse Events

All AEs should be captured on the eCRF from the time of signing of ICF through the final Follow-Up Visit/phone call. AEs considered at least possibly related to KAN-101 should be followed until resolution, return to baseline, or deemed chronic or stable.

All serious adverse events (SAEs) will be immediately reported to the Sponsor from the time of signing the ICF through the Follow-Up Visit/phone call or until the patient has been deemed to be a screen failure. After completion of the AE reporting period (ie, through the final Follow-Up Visit/phone call), only SAEs attributed to KAN-101 must be reported to the Sponsor.

See [Section 11.2](#) for a full description of the collection and reporting of AEs during this study.

6.2. Safety Follow-up Visit

All patients in Part A will have a final Follow-Up at D21 (± 1), 20 days after the single administration of KAN-101.

All patients in Part B will have a final Follow-Up phone call at D28 (± 3), approximately 20 days after the final administration of KAN-101 on D7.

Ongoing AEs considered at least possibly related to KAN-101 treatment should be followed until resolution, return to baseline, or are considered stable or chronic.

7. CONCOMITANT MEDICATIONS

7.1. Prohibited Concomitant Therapies

During the study period, any additional therapies to treat CeD or other investigational agents are prohibited, including biologic or non-biologic immunosuppressive or immunomodulatory therapies. In addition, non-investigational immunosuppressive and immunomodulatory therapies are prohibited (eg, systemic corticosteroids). Patients should avoid the use of probiotic supplements during the study period. All vaccines are prohibited for at least 4 weeks prior to dosing and during the study period.

7.2. Permitted Concomitant Therapies

All patients are required to maintain a GFD during the study. Any other medication that is considered necessary for the patient's welfare that is not expected to interfere with the evaluation of KAN-101 may be given at the discretion of the Investigator. In cases involving concomitant therapies whose predicted interference with KAN-101 is unknown to the Investigator, the Sponsor should be contacted for discussion. Patients being treated for IBS symptomology will be allowed to continue therapy (eg, dicyclomine) unless the drug is specifically prohibited ([Section 7.1](#)).

Antidiarrheal (eg loperamide) or antiemetics (eg metoclopramide) may be used during the GC if warranted by symptomology unless the drug is specifically prohibited ([Section 7.1](#)).

Any medication (including over the counter or prescription medications, vitamins, and/or herbal supplements) that the patient receives after enrollment through the last study visit must be recorded on the eCRF.

8. CONTRACEPTION AND PREGNANCY

The effects of KAN-101 on conception, pregnancy, and lactation are unknown.

At screening, all women who are not surgically sterile or postmenopausal must agree to use at least 2 medically acceptable methods of birth control (defined as the use of an intrauterine device, a barrier method with spermicide, condoms, any form of hormonal contraceptives, or partner sterility) for the duration of the study. WCBP who practice complete sexual abstinence are NOT required to commit to use of 2 methods of birth control. Complete sexual abstinence is only acceptable when it is the usual/preferred lifestyle of the subject and has been so for at least 3 months prior to Screening. Periodic abstinence, calendar timing methods of contraception, or withdrawal are NOT acceptable methods of contraception.

At screening, all men who are not sterile (biologically or surgically) must commit to the use of 1 reliable method of birth control (e.g. condoms with spermicide, sterile partner) for the duration of the study.

A serum pregnancy test will be administered during screening for all WCBP. A serum or urine pregnancy test will be administered to all WCBP prior to each dose of study drug and must be confirmed negative before administration of study drug.

9. OTHER RESTRICTIONS RELATED TO COVID-19

Patients will be advised to adhere to local requirements for reduction of the severe acute respiratory syndrome coronavirus 2 (SARS-CoV-2) exposure while ambulatory. All patients should be called 1 day prior to every visit for assessing COVID-19 signs and symptoms and asked not to attend the site if infection is suspected. In addition, patients will be asked whether they have had any contact with a person who has a confirmed infection. If applicable, patients will be referred to the local health care system. Physical distancing and person-to-person contact restrictions should be applied and explained to patients while staying at the study site, if required by local requirements. Where physical distancing is not possible, study participants will be asked to use face masks and/or gloves, if deemed appropriate by the Investigator and site staff and guided by local requirements.

10. KAN-101 MATERIALS AND MANAGEMENT

10.1. KAN-101 and Placebo

CCI

10.2. Dosage and Administration

KAN-101 is provided as a frozen concentrated solution CCI which will be diluted into 250 mL normal saline.

Administration will be by IV infusion over approximately 30 minutes.

For Part A, patients will receive a single IV infusion of KAN-101 only (no PBO).

For Part B, patients will receive 3 IV infusions, each spaced 3 days apart, of a given dose of either KAN-101 or PBO. All doses will be prepared as outlined in the KAN-101-01 Pharmacy Manual by an unblinded pharmacist.

Study treatment (KAN-101 or PBO) should be administered over 30 minutes under the supervision of a physician or other medically qualified study personnel experienced in the use of IV agents and in a facility equipped to manage medical emergencies. In the event of a Grade 3 infusion-related reaction (IRR), the total infusion duration may be increased to 1 hour (please see [Section 10.5](#) for more information). In cases where a temporary interruption is required, the total infusion should be completed within 24 hours of thawing the drug product. See [Section 10.5](#) for detailed guidance regarding infusion administration interruptions due to infusion reactions.

Please refer to the KAN-101 Pharmacy Manual for detailed administration instructions.

10.3. Storage

KAN-101 is supplied in vials for single use. KAN-101 is to be stored at -20°C and protected from light in a temperature-monitored, locked freezer. Additional details on storage conditions are available in the KAN-101 Pharmacy Manual.

10.4. Post-Infusion Medications

No specific post-infusion medications are required for KAN-101, but may be administered at the discretion of the Investigator.

10.5. Infusion-Related Reactions

If an IRR occurs during KAN-101 administration, the following treatment recommendations are provided and may be modified per local treatment standards and guidelines as appropriate.

- Grade 1 (mild): Infusion rate modification not indicated. Administer symptomatic treatment (eg, antihistamines, antipyretics, antiemetics) as needed. Closely monitor patient until resolution. Prophylaxis with diphenhydramine 50 mg (or equivalent) and/or acetaminophen/paracetamol 325 to 1000 mg is recommended at least 30 min prior to future KAN-101 infusions
- Grade 2 (moderate): Slow infusion to $\leq 50\%$ of the original infusion rate and treat symptoms with appropriate medical therapy, including but not limited to antihistamines, antipyretics, and analgesics. Increase monitoring of vital signs as medically indicated until patient is deemed stable. Prophylaxis with diphenhydramine 50 mg (or equivalent) and/or acetaminophen/paracetamol 325 to 1000 mg is recommended at least 30 min prior to future KAN-101 infusions
- Grade 3 (severe): Stop infusion and institute appropriate symptom-directed therapy, including but not limited to antihistamines, antipyretics, corticosteroids, bronchodilators, and O₂. Increase monitoring of vital signs as medically indicated until patient is deemed stable. If the reaction has not resolved within 6 hours, the remainder of the infusion will not be administered and KAN-101 will be permanently discontinued. Following the completion or termination of a restarted infusion due to an IRR, all patients must be monitored until resolution of symptoms or for 2 hours in the absence of additional symptoms. Prophylaxis with diphenhydramine 50 mg (or equivalent) and/or acetaminophen/paracetamol 325 to 1000 mg is required at least 30 min prior to future KAN-101 infusions. The next infusion should initiate at a rate of 2 hours per dose, or 50% of the rate at which the reaction occurred. If no IRRs are observed within the first 30 minutes, the infusion rate may increase to the 1-hour-per-dose rate as outlined in [Section 10.2](#). Permanently discontinue KAN-101 upon a second occurrence of a Grade 3 or greater infusion reaction.
- Grade 4 (life-threatening): Stop infusion and immediately institute appropriate symptom directed therapy and supportive measures as necessary, including, but not limited to, corticosteroids, bronchodilators, O₂/respiratory support, and vasopressors. Hospitalization and/or intensive care unit admission may be indicated. Permanently discontinue treatment.

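### After a Grade 3 reaction at the 30-minute rate, Section 10.5 gives two starting rates that differ two-fold: one leaves the step-up empty, the other outlasts the hour named in Section 10.2

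*Protocol*

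**What the plan says.** Protocol Section 10.2 fixes the standard infusion: "Study treatment (KAN-101 or PBO) should be administered over 30 minutes". For severe reactions it adds: "In the event of a Grade 3 infusion-related reaction (IRR), the total infusion duration may be increased to 1 hour". It then refers the reader to Section 10.5. It does not say whether the hour applies to the infusion in which the reaction occurred or to a later one, and it mentions no 2-hour infusion.

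Section 10.5, under Grade 3, gives the starting rate for the following infusion: "The next infusion should initiate at a rate of 2 hours per dose, or 50% of the rate at which the reaction occurred". It then allows a step-up: "If no IRRs are observed within the first 30 minutes, the infusion rate may increase to the 1-hour-per-dose rate", and it cites Section 10.2 for that rate. It does not say whether the two starting rates are meant as equivalents or as alternatives, or which applies when. The section opens by allowing its recommendations to be adapted to local standards. Under Grade 2 it slows the running infusion to half its original rate or less.

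Two other sections decide whether a next infusion happens at all. Section 4.6 counts any event of Grade 3 or above assessed as related to KAN-101 as a dose-limiting toxicity (DLT). Section 4.9 gives a Part B patient no more doses after a DLT in the dose-escalation safety monitoring period. Section 4.7 runs that period from the first infusion to the D15 visit, so it covers all three doses.

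**The concern.** The sentence in Section 10.5 puts a fixed duration and a relative rate side by side as if they matched. Against a 30-minute standard infusion they do not. The fixed figure, the relative figure and the step-up would all fit a standard infusion of 1 hour, but the protocol does not describe one.

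The text governs re-dosing after a severe reaction in a first-in-human study with six active patients per Part B cohort. Two sites could follow the same sentence in good faith and start at rates two-fold apart. In a cohort that small, one or two infusions run differently could blur whether a recurrence, or a lower peak concentration, reflects the dose level or the site's reading. The SAP (Section 3.5.2) also builds its nominal PK times on an infusion of about 30 minutes.

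**Working it through.** **Inputs.** Standard duration: 30 minutes per dose (Section 10.2). Starting rate: 2 hours per dose, or 50% of the rate at reaction (Section 10.5). Step-up: to 1 hour per dose after 30 minutes without a reaction (Section 10.5). Extended duration: 1 hour (Section 10.2). For mL/h only, the total volume is assumed to be 250 mL, from "which will be diluted into 250 mL normal saline"; the added drug volume is ignored. The durations do not depend on this assumption.

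**Step 1: do the two starting rates agree?** At half the rate, minutes per dose = (minutes per dose at reaction) / 0.5. The 40-minute row is illustrative.

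| Reaction at | 50% of that rate | 2 h per dose as share of that rate | Ratio of the two starting rates |
|---|---|---|---|
| 30 min per dose | 60 min per dose | 30/120 = 25% | 120/60 = 2.0 |
| 40 min per dose | 80 min per dose | 40/120 = 33% | 120/80 = 1.5 |
| 60 min per dose | 120 min per dose | 60/120 = 50% | 120/120 = 1.0 |

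At the standard rate they differ two-fold. In mL/h: standard 250/0.5 = 500; half of it 250; 2 hours per dose 250/2 = 125. They agree only at 60 minutes per dose.

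**Step 2: how long does each branch take?** With the earliest step-up, total minutes = 30 + (1 − 30/s) × 60, where s is the starting minutes per dose.

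- Half-rate branch, s = 60: 30 + 0.50 × 60 = 60 minutes. The infusion already runs at 1 hour per dose, so the step-up is no increase.
- 2-hour branch, s = 120: 30 + 0.75 × 60 = 75 minutes. A quarter of the dose is in after 30 minutes, and the other three quarters take 45 minutes. Without the optional step-up the total is 120 minutes.

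**Step 3: compare with Section 10.2.** Its only extended duration is 60 minutes. The half-rate branch equals it. The 2-hour branch is 75/60 = 1.25 times it with step-up and 120/60 = 2 times it without.

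**Step 4: who can reach the rule?** Part A gives one dose, so a next infusion exists only in Part B, after the D1 or D4 dose. If the Grade 3 reaction is assessed as related, it is a DLT (Section 4.6) and Section 4.9 ends that patient's dosing. Section 11.2.2 counts a possible relationship as related. The Section 10.5 rule is therefore left for reactions assessed as not related. Yet Section 10.5 makes no such distinction: it sets premedication and a rate for the next infusion, and it reserves permanent discontinuation for a second Grade 3 or greater reaction (or a first that has not resolved within 6 hours).

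**The case against.** The best defence has four parts.

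- **The figures can agree.** If a Grade 2 reaction has already slowed the infusion to half rate, and it then worsens to Grade 3, the reaction occurs at 1 hour per dose. Then 2 hours per dose is exactly half the rate, and the step-up is a real increase. This stands, and Section 10.5 itself can produce the case. It does not cover a Grade 3 reaction at the standard rate.
- **The wording is flexible.** Section 10.2 is permissive and defers to Section 10.5, which allows local modification. This also stands, but freedom to modify a default does not make the default coherent. The Pharmacy Manual may say more; it is not among the documents.
- **The rule is seldom reached.** Sections 4.6 and 4.9 stop dosing after a related Grade 3 event. This narrows the point considerably, but it also exposes a second mismatch, because Section 10.5 plans for re-dosing without that condition.
- **Departures would be visible.** SAP Section 4.9.1 lists actual infusion duration and its difference from 30 minutes. That helps interpretation afterwards but gives no guidance at the bedside.

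A reader might infer three stronger things that the documents do not support. First, that no infusion under Section 10.5 can finish within an hour: the half-rate branch takes exactly 60 minutes. Second, that a site following Section 10.5 violates Section 10.2: "the total infusion duration may be increased to 1 hour" is an allowance, not a ceiling, and it is not tied to a particular infusion. Third, that Section 10.2 confines lengthening to Grade 3: it names Grade 3 as one circumstance, excludes no other, and defers to Section 10.5, which covers Grade 2.

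**Conclusion.** The instruction is wrong as written for a Grade 3 reaction at the protocol's own standard rate. It gives two starting rates that differ by a factor of 2. One makes the step-up empty (60 minutes throughout). The other takes 75 to 120 minutes, while the section cited for the step-up rate mentions only 1 hour and does not say for which infusion. The rule also conflicts with Section 4.9 wherever the reaction is assessed as related.

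These results rest on the 30-minute infusion, on a reaction at that rate, and on reading the next infusion as the patient's next scheduled dose. Few infusions are likely to be affected, all in Part B, and the primary analysis does not depend on the rule. An effect on recurrence or peak concentration is possible but is not quantified here. The reason to act is that a safety instruction should have a single reading.

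**What to change.** Reconcile Protocol Sections 10.2, 10.5 and 4.9 in one amendment:

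- State the starting rate of the infusion after a Grade 3 reaction once, in minutes per dose or mL/h, or say which of the two rates applies when.
- Make the step-up differ from the starting rate, or remove it where it has no effect.
- Say which infusion the 1 hour in Section 10.2 refers to, and make the stated duration one that the sequence in Section 10.5 can produce.
- Say how Section 10.5 applies after a DLT, so that it and Section 4.9 give the same answer on further dosing.

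The sponsor chooses the values and the rule; this review takes no view on which rate or rule is right. The Pharmacy Manual should be checked for consistency with the result. The cost is wording, with no added patients, visits or procedures.

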10.6. Drug Accountability

The Investigator or designee is responsible for taking an inventory of each shipment of KAN-101 received and comparing it with the accompanying drug order form. All unused KAN-101 will be retained at the site. After full drug accountability and reconciliation, the Investigator will dispose of any KAN-101 at the clinical study site per site procedures, or if necessary, all KAN-101 will be returned to the Sponsor or its designee. Disposition of all KAN-101 should be documented, including any KAN-101 that is lost or damaged.

10.7. Assignment to Treatment

Once a patient has met all entry criteria, the Interactive Response Technology (IRT) will be used to generate a distinct patient identifier. If a patient discontinues from the study, the patient identifier will not be reused and the patient will not be allowed to re-enter the study.

In Part A, patients will be assigned to receive open-label KAN-101 at a dose level based on the next available spot in the cohort(s) currently being enrolled.

In Part B, the first 2 eligible patients within each cohort will be randomized via IRT in a 1:1 ratio to receive either KAN-101 or PBO. After completion of the sentinel dosing, the remaining 6 patients in each cohort will be randomized 5:1 to receive KAN-101 or PBO.

11. SAFETY DATA COLLECTION, RECORDING, AND REPORTING

11.1. Adverse Events

11.1.1. Definition of an Adverse Event

An AE is defined as any untoward medical occurrence associated with the use of a drug, or with study participation, whether or not consider related to study treatment.

An AE can therefore be any unfavorable and unintended sign (eg, an abnormal laboratory finding), symptom, or disease temporally associated with the use of the medicinal product, whether or not considered related to the medicinal product.

AEs include worsening of a pre-existing medical condition as well as CS changes from baseline laboratory values/conditions. Worsening of the preexisting medical condition (eg, diabetes, hypertension) means that it has increased in severity, frequency, and/or duration, and/or has an association with a significantly worse outcome. A pre-existing condition that has not worsened during the study is not considered an AE.

11.1.2. Definition of a Serious Adverse Event

An SAE is any untoward medical occurrence that at any dose:

- Results in death
- Is immediately life-threatening
- Requires inpatient hospitalization or prolongation of existing hospitalization.
 - Elective or pre-planned treatment for a pre-existing condition that is unrelated to the indication under study and has not worsened since signing the ICF (documented as medical history on the eCRF) is not considered an SAE
 - Scheduled therapy for the target disease of the study, including admissions for transfusion support or convenience, is not considered an SAE
- Results in persistent or significant disability/incapacity
- Results in congenital anomaly/birth defect
- Is considered an important medical event
 - If an AE does not meet 1 of the serious criteria, but the Investigator or Sponsor considers an event to be clinically important, the event could be classified as an SAE under the criterion of an ‘Important Medical Event’. Examples of such medical events may include allergic bronchospasm requiring intensive treatment in an emergency room or at home, or blood dyscrasias or convulsions that do not result in inpatient hospitalization.

